#### **Definition of serious adverse events**

A serious adverse event is an AE occurring during any study phase (i.e., screening, run-in, treatment, wash-out, follow-up), at any dose of the study drugs that fulfills one or more of the following criteria:

- Results in death
- Is immediately life-threatening
- Requires in-patient hospitalization or prolongation of existing hospitalization
- Results in persistent or significant disability or incapacity

Quad-Shot Radiotherapy in Combination with Immune Checkpoint Inhibition for Advanced/Recurrent Head and Neck Cancer  
Wake Forest Baptist Comprehensive Cancer Center  
WFBCCC60320

- Is a congenital abnormality or birth defect in offspring of the subject
- Is an important medical event that may jeopardize the patient or may require medical intervention to prevent one of the outcomes listed above.
- Medical or scientific judgment should be exercised in deciding whether expedited reporting is appropriate in this situation. Examples of medically important events are intensive treatment in an emergency room or at home for allergic bronchospasm, blood dyscrasias, or convulsions that do not result in fatality

The causality of SAEs (their relationship to all study treatment/procedures) will be assessed by the investigator(s).

**Definition of adverse events of special interest (AESI)**

An adverse event of special interest (AESI) is one of scientific and medical interest specific to understanding of the Investigational Product and may require close monitoring. An AESI may be serious or non-serious.

AESIs for pembrolizumab include but are not limited to events with a potential inflammatory or immune-mediated mechanism and which may require more frequent monitoring and/or interventions such as steroids, immunosuppressants and/or hormone replacement therapy. These AESIs are being closely monitored in clinical studies with pembrolizumab monotherapy and combination therapy. An immune-related adverse event (irAE) is defined as an adverse event that is associated with drug exposure and is consistent with an immune-mediated mechanism of action and where there is no clear alternate aetiology. Serologic, immunologic, and histologic (biopsy) data, as appropriate, should be used to support an irAE diagnosis. Appropriate efforts should be made to rule out neoplastic, infectious, metabolic, toxin, or other etiologic causes of the irAE.

AESIs observed with pembrolizumab include:

- Colitis
- Pneumonitis
- ALT/AST increases / hepatitis / hepatotoxicity
- Neuropathy / neuromuscular toxicity (i.e. events of encephalitis, peripheral motor and sensory neuropathies, Guillain-Barré, and myasthenia gravis)
- Endocrinopathy (i.e. events of hypophysitis, adrenal insufficiency, and hyper- and hypothyroidism)
- Dermatitis
- Nephritis
- Pancreatitis (or labs suggestive of pancreatitis - increased serum lipase , increased serum amylase)

Patients should be thoroughly evaluated to rule out any alternative etiology (e.g., disease progression, infections etc.)

Steroids should be considered in the absence of clear alternative etiology even for low grade events (Grade 2), in order to prevent potential progression to higher grade event.

Quad-Shot Radiotherapy in Combination with Immune Checkpoint Inhibition for Advanced/Recurrent Head and Neck Cancer  
Wake Forest Baptist Comprehensive Cancer Center  
WFBCCC60320

### **Severe and Fatal Immune-Mediated Adverse Reactions**

Immune-mediated adverse reactions, which may be severe or fatal, can occur in any organ system or tissue and usually occur during treatment; however, they can also occur after discontinuation. Early identification and management are essential to ensuring safe use of PD-1-blocking antibodies. Monitor for symptoms and signs of immune-mediated adverse reactions. Evaluate clinical chemistries, including liver tests and thyroid function tests, at baseline and periodically during treatment. Institute medical management promptly to include specialty consultation as appropriate.

In general, withhold pembrolizumab for Grade 3 or 4 and certain Grade 2 immune-mediated adverse reactions. Permanently discontinue pembrolizumab for Grade 4 and certain Grade 3 immune-mediated adverse reactions. For Grade 3 or 4 and certain Grade 2 immune-mediated adverse reactions, administer corticosteroids (1 to 2 mg/kg/day prednisone or equivalent) or other appropriate therapy until improvement to Grade 1 or less followed by a corticosteroid taper over 1 month. Consider administration of other systemic immunosuppressants in patients whose immune-mediated adverse reaction is not controlled with corticosteroids. Institute hormone replacement therapy for endocrinopathies as warranted.

**Immune-mediated pneumonitis:** Immune-mediated pneumonitis occurred in about 2.5% of the patients treated with immune checkpoint inhibitors and leads to permanent discontinuation of the drug in about half of the patients. Systemic corticosteroids are required in all patients with pneumonitis. Withhold pembrolizumab for Grade 2, and permanently discontinue for Grade 3 or 4. Resume in patients with complete or partial resolution (Grade 0 to 1) after corticosteroid taper.

**Immune-mediated colitis:** Immune-mediated colitis occur in about 1% of patients receiving immune checkpoint inhibitors leading to permanent discontinuation pembrolizumab in a small percent of patients. Systemic corticosteroids are required in all patients with colitis. Withhold pembrolizumab for Grade 2 or 3, and permanently discontinue for Grade 4. Resume in patients with complete or partial resolution (Grade 0 to 1) after corticosteroid taper.

**Immune-mediated hepatitis:** Immune-mediated hepatitis occurred in general in about 2% of patients receiving immune checkpoint inhibitors. Systemic corticosteroids are required in all patients with hepatitis. Withhold pembrolizumab if AST or ALT increases to more than 3 and up to 10 times the upper limit of normal (ULN) or if total bilirubin increases up to 3 times the ULN. Permanently discontinue pembrolizumab if AST or ALT increases to more than 10 times the ULN or total bilirubin increases to more than 3 times the ULN. Resume in patients with complete or partial resolution (Grade 0 to 1) after corticosteroid taper.

**Immune-mediated endocrinopathies:** Withhold pembrolizumab if clinically necessary for Grade 2, 3, or 4.

- **Adrenal insufficiency:** Adrenal insufficiency occurs in less than 1% of patients receiving immune checkpoint inhibitors
- **Hypophysitis:** Hypophysitis, which can result in hypopituitarism, occurs very rarely, around 0.2% of patients on immune checkpoint inhibitors
- **Hypothyroidism:** Hypothyroidism occurred in about 6% of patients receiving immune checkpoint inhibitors it is not necessary for the patients to discontinue hormone replacement therapy
- **Hyperthyroidism:** Hyperthyroidism occur in about 1.5% of patients receiving immune checkpoint inhibitors.
- **Type 1 diabetes mellitus:** Type 1 diabetes mellitus, which can present with diabetic ketoacidosis, occurred in less than 1% of patients undergoing immune checkpoint inhibitors and leads to permanent discontinuation of the drug in exceptional cases.

Quad-Shot Radiotherapy in Combination with Immune Checkpoint Inhibition for Advanced/Recurrent Head and Neck Cancer  
Wake Forest Baptist Comprehensive Cancer Center  
WFBCCC60320

**Immune-mediated nephritis with renal dysfunction:** Immune-mediated nephritis occurs in about 0.5% of patients receiving immune checkpoint inhibitors and leads to permanent discontinuation of the drug in about half of the patients. Systemic corticosteroids are required in all patients with nephritis. Withhold pembrolizumab for Grade 3, and permanently discontinue for Grade 4. Resume in patients with complete or partial resolution (Grade 0 to 1) after corticosteroid taper.

**Immune-mediated dermatologic adverse reactions:** Immune-mediated dermatologic reactions, including erythema multiforme and pemphigoid, occur in about 2% of patients receiving immune checkpoint inhibitors. In addition, SJS and TEN have been observed with immune checkpoint inhibitors. Systemic corticosteroids are required in all patients with dermatologic reactions. Withhold pembrolizumab for Grade 3, and permanently discontinue for Grade 4. Resume in patients with complete or partial resolution (Grade 0 to 1) after corticosteroid taper.

**Other immune-mediated adverse reactions:** The following clinically significant immune-mediated adverse reactions occur at an incidence of <1% of patients who receive immune checkpoint inhibitors. Severe or fatal cases have been reported for some of these adverse reactions. Withhold pembrolizumab for Grade 3, and permanently discontinue for Grade 4. Resume in patients with complete or partial resolution (Grade 0 to 1) after corticosteroid taper.

- **Neurological:** Meningitis, encephalitis, myelitis and demyelination, myasthenic syndrome/myasthenia gravis, Guillain-Barré syndrome, nerve paresis, and autoimmune neuropathy
- **Cardiovascular:** Myocarditis, pericarditis, and vasculitides
- **Ocular:** Uveitis, iritis, and other ocular inflammatory toxicities. Some cases can be associated with retinal detachment. Various Grades of visual impairment to include blindness can occur. If uveitis occurs in combination with other immune-mediated adverse reactions, consider a Vogt-Koyanagi-Harada-like syndrome, as this may require treatment with systemic corticosteroids to reduce the risk of permanent vision loss
- **Gastrointestinal:** Pancreatitis to include increases in serum amylase and lipase levels, gastritis, and duodenitis
- **Musculoskeletal and connective tissue:** Myositis, rhabdomyolysis, and associated sequelae, including renal failure, arthritis, and polymyalgia rheumatica
- **Hematological and immunological:** Hemolytic anemia, aplastic anemia, hemophagocytic lymphohistiocytosis, systemic inflammatory response syndrome, histiocytic necrotizing lymphadenitis (Kikuchi lymphadenitis), sarcoidosis, immune thrombocytopenic purpura, and solid organ transplant rejection

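### Section 8.1 requires systemic steroids for five immune reactions without stating a grade, which is broader than its own general rule, and its bilirubin hold for immune hepatitis has no lower bound

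*Combined protocol and SAP*

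**What the plan says.** Section 8.1, under Severe and Fatal Immune-Mediated Adverse Reactions, opens with a general rule: "For Grade 3 or 4 and certain Grade 2 immune-mediated adverse reactions, administer corticosteroids (1 to 2 mg/kg/day prednisone or equivalent") or other suitable treatment. This continues until the event is at Grade 1 or below, "followed by a corticosteroid taper over 1 month".

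The organ paragraphs that follow drop the grade. For pneumonitis: "Systemic corticosteroids are required in all patients with pneumonitis". For colitis: "Systemic corticosteroids are required in all patients with colitis". The hepatitis and nephritis paragraphs carry the same sentence with the organ changed, and the skin paragraph reads "Systemic corticosteroids are required in all patients with dermatologic reactions". Each paragraph then gives graded or laboratory criteria for holding and stopping the drug. For pneumonitis these are "Withhold pembrolizumab for Grade 2, and permanently discontinue for Grade 3 or 4", and for colitis "Withhold pembrolizumab for Grade 2 or 3, and permanently discontinue for Grade 4". For nephritis and skin the hold starts at Grade 3.

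Earlier in Section 8.1, the text on adverse events of special interest treats Grade 2 as low grade. It asks that steroids be considered at that level when no other cause is clear.

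For hepatitis, the AST/ALT hold runs from above 3 to 10 x ULN. The bilirubin hold in the same sentence covers an increase of up to 3 x ULN, with no starting value. Section 3.1.8.4 admits patients with bilirubin up to 1.5 x ULN.

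**The concern.** Drug holds and stops carry a grade or a laboratory threshold, but the steroid instruction beside them does not. A site following the organ text gives mandatory systemic steroids for a Grade 1 reaction, the grade at which the general rule begins the taper. For skin and nephritis, where the hold starts at Grade 3, the patient would take steroids at Grade 1 or 2 while pembrolizumab continues.

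Unneeded steroids are not neutral in this trial. Section 4.4.7.3 treats systemic doses above 10 mg/day of prednisone as excluded immunosuppression except in listed uses, such as managing drug-related events. Objective 2.3.1 studies immune activation.

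The bilirubin wording can work the other way and stop the drug too readily. Once immune-mediated hepatitis is diagnosed, a bilirubin rise to a level acceptable at entry is enough for a hold, and the drug resumes only after a steroid taper.

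**Working it through.** There is no planned figure to reproduce. The check compares the rules with one another and then bounds how many patients they can reach.

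**Steroid rules by grade (all Section 8.1)**

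| Grade | General rule | Special-interest text | Five organ paragraphs |
|---|---|---|---|
| 1 | Not called for; taper begins here | Not mentioned | Required |
| 2 | Certain events, not listed | Consider | Required |
| 3-4 | Give | No separate rule | Required |

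The rules agree at Grade 3-4. At Grade 2 they differ in strength (consider against require), although the organ text could be supplying the unlisted Grade 2 events. At Grade 1 only the organ text calls for steroids.

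**Hold and stop criteria, and the protocol's rates (Section 8.1)**

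| Reaction | Hold | Stop | Rate |
|---|---|---|---|
| Pneumonitis | Grade 2 | Grade 3-4 | 2.5% |
| Colitis | Grade 2-3 | Grade 4 | 1% |
| Hepatitis | AST/ALT >3 to 10 x ULN, or bilirubin up to 3 x ULN | AST/ALT >10 x ULN, or bilirubin >3 x ULN | 2% |
| Nephritis | Grade 3 | Grade 4 | 0.5% |
| Skin | Grade 3 | Grade 4 | 2% |

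**Reach of the steroid sentences, 15 patients**

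- Any such reaction, any grade, no overlap assumed: 2.5% + 1% + 2% + 0.5% + 2% = 8.0%, and 15 x 0.080 = 1.2 patients. The chance of at least one in 15 is 1 - 0.92^15 = 71%. This shows how likely the paragraphs are to be used, not how often harm follows.
- For pneumonitis and for nephritis the protocol says the reaction "leads to permanent discontinuation of the drug in about half of the patients". If those cases are Grade 3-4, the steroid rules agree for them. Removing 0.5 x 2.5% + 0.5 x 0.5% = 1.5% leaves 6.5%, and 15 x 0.065 = 0.98 patients.
- The protocol does not split these rates by grade. With a Grade 1 share anywhere from 0 to 100%, the number affected at Grade 1 runs from 0 to 0.98. Nothing in the documents supports a value in between.
- Steroids at Grade 1-2 with the drug continuing (skin plus the remaining nephritis): at most 2% + 0.25% = 2.25%, and 15 x 0.0225 = 0.34 patients.

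**Bilirubin hold**

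- Written range: any increase up to 3 x ULN. Entry range: up to 1.5 x ULN. The two overlap from any rise up to 1.5 x ULN.
- Reach: at the protocol's hepatitis rate, at most 15 x 0.02 = 0.30 patients. The share with only a small bilirubin rise is not given.
- Consequence: the hepatitis paragraph states no taper length. If the general 1-month taper (about 30 days) applies, it exceeds the 21-day dosing interval in Section 4.4.2, so at least one dose is delayed.

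**The case against.** A reader might infer that Section 8.1 contradicts itself. The documents do not support that. The general rule says when to give steroids and nowhere says to withhold them at Grade 1, so both texts can be followed by letting the organ paragraph govern. That objection stands, and the point is therefore a mismatch in scope. It does not remove the problem, because following the organ text is exactly what makes steroids mandatory at Grade 1.

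It can also be said that the heading confines these paragraphs to severe events and that mild events have another route. Section 4.4.6.1 starts with supportive care and favours continuing the same dose if symptoms settle promptly, and Section 8.1 asks that other causes be ruled out. This helps, but only in part. The pneumonitis and colitis paragraphs themselves act at Grade 2, and Section 4.4.6.2 treats unexplained enterocolitis, dermatitis and hepatitis as immune-related at any grade.

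On bilirubin, a reader might infer that any small rise in any patient stops the drug. It does not: the criterion sits under immune-mediated hepatitis and applies once that diagnosis is made. Resumption at Grade 0 to 1 also suggests that a higher starting level was meant, but no such level is written.

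On size, a reader might take the rash frequency in Section 8.1 (20% or more) and count 15 x 0.20 = 3 patients. Not every rash is immune-mediated or Grade 1, so that count is not supported. In the other direction, the rates used here are for checkpoint inhibitors generally. If mild events attributed under Section 4.4.6.2 fall outside those rates, 1.2 of 15 is a guide and not a strict ceiling.

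**Conclusion.** The point holds as a minor safety-wording correction. Five steroid sentences have no grade and are broader than both the general rule and the special-interest text. The bilirubin hold has no lower bound, unlike the AST/ALT hold beside it.

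Few patients, possibly none, are affected: about 1.2 of 15 for any grade of the five reactions, with an unknown Grade 1 share, and at most 0.30 of 15 for the bilirubin hold. These figures assume that the protocol's rates apply to this population and that the reactions do not overlap. Harm is limited because Sections 4.4 and 6.3 leave treatment to standard of care under the treating oncologist, and Section 4.4.6.1 presents its dose guidance as optional. The sample size, the response-rate estimate and its confidence interval are unchanged.

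**What to change.** Amend Section 8.1 as follows:

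- **Pneumonitis and colitis:** require systemic steroids at Grade 2 or higher, matching the grades at which the drug is held.
- **Hepatitis:** require them once the AST/ALT or bilirubin hold threshold is met. The bilirubin threshold must be completed first, or the steroid sentence inherits the gap.
- **Nephritis and skin:** consider them at Grade 2, in line with the special-interest text, and require them at Grade 3 or higher, where the hold starts.
- **Bilirubin hold:** add a lower edge, for example more than 1.5 and up to 3 x ULN. The value 1.5 is borrowed from the entry limit in Section 3.1.8.4, so the sponsor must confirm it.

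The cost is a few words in five sentences and one threshold at the next amendment. No new data are collected, and the analysis and sample size stay as they are.

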#### **Infusion-related reactions**

Severe infusion-related reactions (Grade 3) occur in about 0.2% of patients receiving checkpoint inhibitors. Monitor patients for signs and symptoms of infusion-related reactions. Interrupt or slow the rate of infusion for Grade 1 or 2, and permanently discontinue for Grade 3 or 4.

#### **Embryo-fetal toxicity**

Pembrolizumab can cause fetal harm when administered to a pregnant woman due to an increased risk of immune-mediated rejection of the developing fetus resulting in fetal death. Advise women of the potential risk to a fetus. Advise females of reproductive potential to use effective contraception during treatment with pembrolizumab and for at least 4 months after the last dose.

#### **Adverse reactions**

Quad-Shot Radiotherapy in Combination with Immune Checkpoint Inhibition for Advanced/Recurrent Head and Neck Cancer  
Wake Forest Baptist Comprehensive Cancer Center  
WFBCCC60320

- Serious adverse reactions occurred in 28% of patients. Serious adverse reactions that occurred in ≥2% of patients were cellulitis, sepsis, pneumonia, pneumonitis, and urinary tract infection. The most common Grade 3-4 adverse reactions (≥2%) were cellulitis, sepsis, hypertension, pneumonia, musculoskeletal pain, skin infection, urinary tract infection, and fatigue
- pembrolizumab was permanently discontinued due to adverse reactions in 5% of patients; adverse reactions resulting in permanent discontinuation were pneumonitis, autoimmune myocarditis, hepatitis, aseptic meningitis, complex regional pain syndrome, cough, and muscular weakness
- The most common adverse reactions (incidence ≥20%) were fatigue, rash, and diarrhea

### **Assessment of safety parameters**

#### **Assessment of severity**

Assessment of severity is one of the responsibilities of the investigator in the evaluation of AEs and SAEs. Severity will be graded according to the NCI CTCAE v 5.0.

The determination of severity for all other events not listed in the CTCAE should be made by the investigator based upon medical judgment and the severity categories of Grade 1 to 5 as defined below.

Grade 1 (mild)	An event that is usually transient and may require only minimal treatment or therapeutic intervention. The event does not generally interfere with usual activities of daily living.
Grade 2 (moderate)	An event that is usually alleviated with additional specific therapeutic intervention. The event interferes with usual activities of daily living, causing discomfort but poses no significant or permanent risk of harm to the subject.
Grade 3 (severe)	An event that requires intensive therapeutic intervention. The event interrupts usual activities of daily living, or significantly affects the clinical status of the subject.
Grade 4 (life threatening)	An event, and/or its immediate sequelae, that is associated with an imminent risk of death or with physical or mental disabilities that affect or limit the ability of the subject to perform activities of daily living (eating, ambulation, toileting, etc).
Grade 5 (fatal)	Death (loss of life) as a result of an event.

It is important to distinguish between serious criteria and severity of an AE. Severity is a measure of intensity whereas seriousness is defined by the criteria in Section 10.1.2. A Grade 3 AE need not necessarily be considered an SAE. For example, a Grade 3 headache that persists for several hours may not meet the regulatory definition of an SAE and would be considered a nonserious event, whereas a Grade 2 seizure resulting in a hospital admission would be considered an SAE.

#### **Assessment of relationship**

The Investigator will assess the causal relationship between the IP and each AE and answer “yes” or “no” to the question “Do you consider that there is a reasonable possibility that the event may have been caused by the investigational product?”

For SAEs, causal relationship will also be assessed for other medications and study procedures. Note that, for SAEs that could be associated with any study procedure, the causal relationship is implied as “yes.”

Quad-Shot Radiotherapy in Combination with Immune Checkpoint Inhibition for Advanced/Recurrent Head and Neck Cancer  
Wake Forest Baptist Comprehensive Cancer Center  
WFBCCC60320

When making an assessment of causality, consider the following factors when deciding if there is a “reasonable possibility” that an AE may have been caused by the drug.

- Time Course. Exposure to suspect drug. Has the patient actually received the suspect drug? Did the AE occur in a reasonable temporal relationship to the administration of the suspect drug?
- Consistency with known drug profile. Was the AE consistent with the previous knowledge of the suspect drug (pharmacology and toxicology) or drugs of the same pharmacological class? Or could the AE be anticipated from its pharmacological properties?
- De-challenge experience. Did the AE resolve or improve on stopping or reducing the dose of the suspect drug?
- No alternative cause. The AE cannot be reasonably explained by another etiology such as the underlying disease, other drugs, or other host or environmental factors.
- Laboratory tests. A specific laboratory investigation (if performed) has confirmed the relationship in difficult cases, other factors could be considered such as:
  - Is this a recognized feature of overdose of the drug?
  - Is there a known mechanism?

Causality of “related” is made if, following a review of the relevant data, there is evidence for a “reasonable possibility” of a causal relationship for the individual case. The expression “reasonable possibility” of a causal relationship is meant to convey, in general, that there are facts (evidence) or arguments to suggest a causal relationship. The causality assessment is performed based on the available data including enough information to make an informed judgment. With limited or insufficient information in the case, it is likely that the event(s) will be assessed as “not related.” Causal relationship in cases where the disease under study has deteriorated due to lack of effect should be classified as no reasonable possibility.

